## **12.3 Clinical Laboratory Tests**

Safety laboratory assessments will be presented in patient listings.

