8.4 ELICITING AND REPORTING ADVERSE EVENTS

All adverse events, regardless of severity, which occur during the study, will be documented in the study progress notes, and the "Adverse Event" case report form will be completed. This includes both serious and non-serious events. Adverse events occurring from the time of the first dose will be captured.

All adverse events noted by study staff or volunteered by study patients at any time will be recorded. The PI or a qualified designated staff physician will conduct clinical assessments of all patients at each scheduled clinic visit. In addition, patients will be queried about any adverse symptoms they have experienced since the previous study visit. In order to avoid bias in eliciting events, suggestive questioning of the patients shall not occur.

A laboratory abnormality will be reported on the "Adverse Event" case report form only if it is the main causative factor of an SAE, requires a therapeutic intervention, is the reason for a patient coming off study, or meets DLT criteria. Record the highest grade of the laboratory abnormality with start and stop dates associated with that grade. Laboratory values for hematology and serum chemistry parameters will be collected during the time the patient is on study to facilitate duration of worst CTCAE grade per cycle change-from-baseline analyses and overall worst CTCAE grade during the study. Any laboratory parameters assessed outside the per-protocol visits (ie, interim labs) will be recorded as 'Unscheduled Laboratory Assessments' in the database.

Adverse events will be reported and described in terms of intensity, seriousness and causality, based on the PI's judgment using protocol-defined definitions. Necessary counter measures will also be reported on the appropriate case report form used to collect concomitant medications.

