11.10.2 Laboratory Tests

Laboratory data will be summarized for the observed values at each scheduled assessment, together with the corresponding changes from baseline (the value obtained prior to dosing on Day 1 of Cycle 1) using descriptive statistics.

For those analytes with NCI CTCAE v5.0 severity criteria are specified, abnormal laboratory values will be summarized by shift tables displaying numerical values and percentages classified by Baseline grade (ie, grade prior

to dosing on Day 1 of Cycle 1) and maximum grade on treatment. All laboratory data will be presented in listings.

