11.10.3 Vital Signs and Physical Examination Findings

Vital signs data will be summarized by the observed values at each scheduled assessment, together with the corresponding changes from baseline using descriptive statistics.

Physical examination findings will be presented in data listings.

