### **3.7 Study Endpoints**

#### **3.7.1 Safety Endpoints**

##### Phase 1b

Safety and tolerability of alvocidib when administered in sequence after DEC (during dose escalation) or AZA will be assessed by analyzing DLTs, MTD, and incidence rates of treatment-emergent adverse events (TEAEs) summarized within treatment group(s) at the MedDRA preferred term and primary system organ class levels. Similar summaries will be made for subsets of AEs such as (1) those judged by the Investigator to be related to study treatment, and (2) serious adverse events (SAEs). Adverse events will be graded according to NCI CTCAE v5.0. Mortality (all causes) will be calculated

Other routine safety assessments (i.e., physical examinations, vital sign measurements, and clinical laboratory testing (hematology and chemistry) will be evaluated as measures of safety and tolerability for the entire study duration. These assessments will be summarized by shift tables and treatment group using mean, standard deviation, median, minimum and maximum changes from baseline values.

##### Phase 2

During the Phase 2 study, tolerance and toxicity will be assessed through evaluation of physical examinations, vital signs, laboratory studies, solicited and unsolicited adverse events, and all causes of mortality at 30 and 60 days.

Routine safety assessments will be summarized by shift tables using mean, standard deviation, median, minimum and maximum changes from baseline values.

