## **12.4 Vital Signs and Weight**

Vital signs data will be presented in patient listings.

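### SAP 3.7.1 promises laboratory and vital-sign shift tables but SAP 12.3-12.4 deliver listings only, so graded laboratory abnormalities kept off the AE form have no summary rate

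*SAP*

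**What the plan says.** - **SAP 3.7.1 (Phase 1b).** For "physical examinations, vital sign measurements, and clinical laboratory testing (hematology and chemistry" the SAP states: "These assessments will be summarized by shift tables and treatment group using mean, standard deviation, median, minimum and maximum changes from baseline values". Phase 1b is the only part of the study that enrolled.
- **SAP 12.3 and 12.4.** For laboratory data: "Safety laboratory assessments will be presented in patient listings". For vital signs: "Vital signs data will be presented in patient listings". No other SAP section specifies a laboratory or vital-sign table.
- **Protocol 11.10.2.** For analytes with CTCAE criteria, "abnormal laboratory values will be summarized by shift tables displaying numerical values and percentages classified by Baseline grade" and by maximum grade on treatment. Protocol 7.1 also promises shift tables.
- **Protocol 11.10.3.** "Vital signs data will be summarized by the observed values at each scheduled assessment", together with changes from baseline.
- **Protocol 8.4.** A laboratory abnormality goes on the adverse event "case report form only if it is the main causative factor of an SAE, requires a therapeutic intervention", is why the patient comes off study, or meets DLT criteria. The same paragraph says laboratory values are collected so that worst CTCAE grade can be analyzed per cycle and overall.
- **Protocol 8.3.** Myelosuppression and its complications, with anemia and thrombocytopenia named, are not reported as SAEs but go on the AE form and are summarized in the reports.
- **Protocol 11.1 and SAP Section 16.** The protocol lets the SAP change the analysis if the change is clearly documented there. Section 16 says the SAP supersedes the protocol's statistics and lists no change.

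**The concern.** The protocol's scheme has two parts: a restricted AE form, and a grade-based summary of the measured values for everything else. SAP 12.3 drops the second part and leaves the first as it was. Because the SAP supersedes the protocol's statistical text, the protocol's shift tables do not fill the gap.

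The gap bears on toxicity of the kind this drug is known for. Protocol 2.6 names five Grade 3-4 events from the earlier 30- to 60-minute infusion experience, and four of them are laboratory findings: lymphocytopenia, neutropenia (dose-limiting there), hypophosphatemia and hyperglycemia. Protocol Table 4 reports hyperbilirubinemia in 6/55 (11%) in an earlier hybrid-schedule study. A report with no table of worst laboratory grade leaves the reader to build those rates by hand.

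**Working it through.** No formula applies. The check sets the texts side by side and then follows each kind of laboratory abnormality to the output where it would appear.

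**1. Promise against output**

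| Data | SAP 3.7.1 | Protocol 11.10 | SAP Section 12 |
|---|---|---|---|
| Laboratory | Shift tables; change from baseline | 11.10.2: values and changes by visit; baseline grade by maximum grade | 12.3: listing |
| Vital signs | Shift tables; change from baseline | 11.10.3: values and changes by visit | 12.4: listing |
| Physical examination | Shift tables; change from baseline | 11.10.3: listing | 12.8: listing |

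SAP 3.7.1 disagrees with SAP Section 12 on all three rows. The protocol's Section 11.10 disagrees with SAP Section 12 on the first two.

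**2. Does early termination explain the removal?** SAP Section 1 drops inferential analysis of efficacy because of low enrollment. SAP 15.1 extends this to safety but keeps descriptive statistics in summary tables. A shift table is descriptive. When SAP Section 11 moves hematologic improvement to listings it gives a reason (a check-all-that-apply form); 12.3 and 12.4 give none.

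**3. Where each kind of laboratory abnormality goes**

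- *Meets at least one of the four criteria in Protocol 8.4.* It reaches the AE form and so the TEAE tables by preferred term, grade and cohort. Examples are a potassium rise that is treated (Protocol 4.5.1.1.3 recommends treatment from above 4.0 mEq/L), Grade 4 chemistry at least possibly drug related, AST or ALT at least 3x ULN with bilirubin above 2x ULN, and a Grade 3 liver test taking more than 7 days to resolve (Protocol 4.5.3).
- *Meets none and is not myelosuppression.* It appears in listings only. By the protocol's own DLT rules this can include an untreated Grade 3 AST, ALT, bilirubin or alkaline phosphatase that resolves within 7 days without meeting the combined criterion, and other untreated Grade 3 chemistry changes that resolve within 48 hours, provided neither causes an SAE or withdrawal.
- *A cytopenia that meets none.* Protocol 8.3 puts it on the AE form; Protocol 8.4, which makes no exception for hematology, keeps it off. Grade 4 neutropenia lasting less than 42 days is an example: it is not a DLT, and because routine growth factor is not allowed (Protocol 4.6.2.2) an uncomplicated episode may need no intervention. Section 8.3 covers neutropenia itself only under the general term myelosuppression. Two sites following the text in good faith could record it differently.

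The tumor lysis table in SAP 12.2 does not close the gap. It is drawn from AE records and limited to events judged related.

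**4. Size**

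- Planned AE tables: 7 in SAP 12.1 + 3 in SAP 12.2 = 10. Planned laboratory tables: 0.
- Patients: 3 + 3 + 3 + 4 + 3 + 4 = 20. One patient is 1/3 = 33% or 1/4 = 25% of a cohort, and 1/20 = 5% of the total.
- The number of abnormalities in the second and third groups cannot be derived from the documents.

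**The case against.** The best defense is that Section 12 is the specific analysis section and should prevail over 3.7.1, which repeats the protocol's endpoint text. The SAP says it reflects Amendment 4 along with the current study status, and it supports a synoptic report on 20 patients. The listings disclose the values, and with 3 or 4 patients per cohort they can be counted by hand. On this view, correcting 3.7.1 and Section 16 is enough. Much of this stands: it limits the seriousness of the point, and it justifies leaving vital signs as listings. It does not supply the missing laboratory rate, and the SAP nowhere gives this reasoning for laboratory data.

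A reader might also infer three stronger things, which the documents do not support.

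- *That most laboratory toxicity is kept off the AE form.* Protocol 8.4 is a conditional rule with four ways in, and no document gives the share that fails it.
- *That the report would contain no Grade 3-4 cytopenia incidence.* Protocol 8.3 directs myelosuppression to the AE form, and SAP 12.1 tabulates AEs by grade. The problem is possible inconsistency, not total absence.
- *That the dose decision is compromised.* The MTD rests on DLTs, and DLT-level laboratory events must go on the AE form. Protocol 11.10 gives the dose escalation committee the complete safety profiles. The sponsor closed the study after a portfolio review, with no patients in Expansion or Phase 2.

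**Conclusion.** The point holds as a reporting defect that should be corrected. SAP 3.7.1 and SAP 12.3-12.4 contradict each other. The summaries promised in the protocol are removed without being recorded in Section 16. Graded laboratory abnormalities outside the four Protocol 8.4 criteria have no summary rate, and AE-based cytopenia rates may be inconsistent because 8.3 and 8.4 conflict. The effect is on how completely laboratory safety is described; the MTD assessment and the availability of the individual data are not affected.

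This rests on two assumptions. The table shells that SAP 8.4 calls part of the SAP are not in the text available; if they contain a laboratory shift table, the defect shrinks to a conflict between the shells and 12.3. It also assumes that at least some sites applied the restriction in Protocol 8.4 as written.

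**What to change.** In SAP 12.3, add one descriptive table of baseline CTCAE grade by worst on-treatment grade for graded hematology and chemistry analytes, including the tumor-lysis analytes, by cohort and total. Show counts beside percentages. State which baseline applies, since SAP 8.6 and Protocol 11.10.2 word it differently. Include unscheduled values, which SAP 8.4 already allows for summaries of maximum post-dose values. Use this table for cytopenia rates in the report, because it does not depend on how a site read Protocol 8.3 and 8.4.

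Leave vital signs and physical examinations as listings, correct 3.7.1 to match, and record in Section 16 what was dropped from the protocol and why.

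The cost is one extra programmed table from data already collected, plus two text edits. The downside is small cells of 3 or 4 patients per cohort, so the table should be read as counts.

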## **12.4 Vital Signs and Weight**

Vital signs data will be presented in patient listings.

## **12.5 12-Lead Electrocardiogram (ECG)**

ECG data will be presented in patient listings.

## **12.6 ECHO or MUGA Scan**

ECHO or MUGA scan data will be presented in patient listings.

## **12.7 ECOG Performance Status**

ECOG assessments will be presented in the patient listings.

## **12.8 Physical Examination and Pregnancy Test**

The physical examination data and pregnancy test results will be presented in patient listings.

## **13. PHARMACOKINETIC (PK) ANALYSIS**

Plasma concentrations of alvocidib will be summarized by descriptive statistics, including mean, n, standard deviation, coefficient of variation, minimum, maximum, and median. Prior to analysis of study samples, the assay sensitivity, specificity, linearity, and reproducibility will be documented.

Parameters to be assessed include the time to Cmax (Peak time, Tmax) and the area under the plasma concentration versus time curve (AUC) from time 0 to 24 hours post-dose (AUC0-24), the maximum observed plasma concentration (Cmax), half life (t1/2), AUC from 0 to time t (AU Ct), AUC from time 0 to infinity (AUC0-inf), and clearance (CL).

Plasma PK analyses for alvocidib and known metabolites, if any, and dose proportionality will be determined during Cycle 1 on Days 8 and 9 (in patients receiving alvocidib following DEC) or Days 10 and 11 (in patients receiving alvocidib following AZA).

PK analyses will be conducted by SDPO or their designee. The results from these analyses are exploratory in nature and may not be included in a clinical study report (CSR).

## **14. PHARMACODYNAMIC (PD) ANALYSIS**

The pharmacodynamic relationship between alvocidib exposure and exploratory biomarkers will be quantified, specifically looking at the correlation between the rate of response (CR/CRi/CRmarrow/PR/HI) and BH3 profiling by flow cytometry with an emphasis on MCL-1 dependence.

The types of biomarkers to be analyzed may include, but are not limited to, nucleic acids, proteins, lipids or metabolites. Biomarker assessments may be used to assess and generate prognostic, predictive pharmacodynamics or surrogate biomarker signatures. These assessments may be explored in the context of MDS or related conditions or drugs of similar class.

PD analyses will be conducted by SDPO or their designee. The results from these analyses are exploratory in nature and may not be included in a clinical study report (CSR).

## **15. COMMITMENT TO GOOD STATISTICAL PRACTICE**

### **15.1 Definition of Good Statistical Practice**

International Conference on Harmonization (ICH) Guidance on Statistical Principles for Clinical Trials (ICH E9) implicitly defines good statistical practice. Good statistical practice includes both appropriate statistical designs to minimize bias and to maximize precision of analysis plus operational excellence to assure credibility of results. The scientific design associated with any clinical trial is found in the protocol and in a more detailed pre-specified statistical analysis plan such as this one.

Due to the early termination of this study and low sample size, efficacy and safety endpoints will not be analyzed via inferential statistical methods. Descriptive statistics will be presented in the summary tables as described in this SAP, and full patient listings will be provided to enable a synoptic clinical study report to be written for this study.

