11. STATISTICAL CONSIDERATIONS

11.1 GENERAL CONSIDERATIONS

Protocol TPI-ALV-102 is a Phase 1b / 2, multicenter, open-label study in which Phase 1b will employ the 3+3 dose-escalation design, dose expansion at MTD/RP2D, and Phase 2 utilizing the Simon 2-stage minimax design [27].

Results of statistical analyses, descriptive statistics, and supporting listings will be presented by study phase (Phase 1b and Phase 2) and within alvocidib dose level. In addition, overall statistics will be calculated for Phase 1b patients across all alvocidib dose levels and for the total study population (ie, regardless of study phase).

Statistical analysis for all safety and efficacy parameters will be primarily descriptive in nature. Categorical variables will be summarized by frequency distributions (number and percentages of patients), continuous variables will be summarized by mean, standard deviation, median, minimum, maximum, and time-to-event variables will be summarized using Kaplan-Meier methods and figures for the estimated median time. No formal statistical hypothesis testing is planned; however, if exploratory analyses are conducted and confidence intervals (CIs) are provided for estimates, the 95% confidence intervals are consistent with a 2-sided 5% significance level. All analyses, summaries, and listings will be performed using SAS software (version 9.4 or higher).

A detailed methodology for summary and statistical analysis of the data collected in this study will be documented in a Statistical Analysis Plan (SAP) that will be finalized prior to database lock. The SAP may modify the data analysis plans outlined in the protocol; and if so, will be clearly documented in the SAP. Any major modifications of the study design or study endpoints and/or its analysis will also be reflected in a protocol amendment.

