11.9 EFFICACY ANALYSIS

The efficacy endpoints include the following:

- Complete Response Rate (CRR) is the percentage of patients achieving a CR, CRi, CRmarrow, PR, or HI. Patients who, for any reason, do not supply bone marrow for response assessment are counted among those not achieving CR/CRi/CRmarrow/PR/HI. CRR will be summarized by number and percentage of patients meeting the definition of CRR along with the corresponding exact 95% confidence intervals.
- Duration of response and time to AML will be summarized by Kaplan-Meier methods (median, 95% CI, number of events, number censored, and Kaplan-Meier figures),
- Hematological improvement and rate of transfusion independence will be summarized using the appropriate descriptive statistics and 95% confidence intervals.
- Overall survival (OS), defined as the time from first dose to death from any cause. OS will be summarized by Kaplan-Meier methods (median, 95% CI, number of events, number censored, and Kaplan-Meier figures).

Descriptive statistics will also be calculated for each secondary measure of efficacy.

- The proportion of MDS patients in the overall population achieving RBC transfusion independence with duration ≥ 84 days (12 weeks) during treatment. Baseline RBC transfusion dependency is defined as an average transfusion requirement of ≥ 2 units/28 days of RBCs without any consecutive 28-day gaps between transfusions for a minimum of 56 days immediately preceding first dose. Transfusion data include the hemoglobin value for which the transfusion was administered and must have been ≤ 10.0 g/dL within 7 days prior to transfusion administration to be counted toward the RBC transfusion-dependent status.
- Platelet transfusion independence with duration ≥ 84 days (12 weeks) will be assessed in the proportion of patients who were platelet transfusion-dependent at baseline. Baseline platelet transfusion requirements are established by the number of platelet transfusions administered during the 56 days immediately preceding and including the date of first dose.

- Erythroid hematologic improvement and platelet hematologic improvement will be assessed according to the 2006 revised IWG criteria [28].

Additional analyses may be performed to assist the sponsor in planning future studies.

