**Efficacy endpoints will not be analyzed via inferential statistical methods due to low enrollment (sample size). Summary tables as described in this SAP and full patient listings will be provided to enable a synoptic clinical study report to be written for this study.**

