**NOTE: For this study, the database will be locked with 20 patients enrolled.**

## **8. DATA PRESENTATION AND HANDLING**

### **8.1 General Summary Table and Individual Patient Data Listing Considerations**

Summary tables for Phase 1b part of this study (the only part with enrollment) will be organized with respect to dose cohort and presented as:

Cohort 1 20mg/m2 (N=3)	Cohort 2 30mg/m2 (N=3)	Cohort 3 45mg/m2 (N=3)	Cohort 4 60mg/m2 (N=4)	Cohort 5 AZA 75mg/m2 + Alvocidib 75mg/m2 (N=3)	Cohort 6 AZA 75mg/m2 + Alvocidib 90mg/m2 (N=4)	Total (N=20)
------------------------------	------------------------------	------------------------------	------------------------------	--	--	-----------------

Alvocidib Phase 1b dose escalation cohort (from low to high) and Total.

Row entries in post text tables are made only if data exists for at least one patient (e.g., a row with all zeros will not appear). The only exception to this rule will apply to tables that summarize the study termination status of patients (e.g., reasons for not completing the study). In this case, zeros will appear for study termination reasons that no patient satisfied. The summary tables will clearly indicate the number of patients to which the data apply and unknown or not performed are distinguished from missing data.

Adverse event preferred terms and body/organ systems and medical history conditions will be coded using the Medical Dictionary for Regulatory Activities (MedDRA®) dictionary Version 21.0 (or later).

Listings will also be sorted by cohort (where applicable) and patient number. Listings will also include visit number, visit date/time and days relative to the initiation of study treatment.

In general, missing data will not be imputed unless otherwise specified. Any imputed or derived data will be flagged in the individual patient data listings. Imputed data will not be incorporated into any raw or primary datasets. These data will be retained in derived analysis datasets.

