### **8.4 Data Presentation Conventions**

Continuous safety variables (e.g., clinical laboratory values and vital signs) will be listed to the same precision as the source data. Derived variables will be calculated and listed using the same precision as the value(s) from which they were derived.

For the tabular reporting of descriptive statistics:

- Continuous variables: the same number of decimal places as in the raw data will be presented when reporting minimum and maximum, 1 more decimal place than in the raw data will be presented when reporting mean and median, and 2 more decimal places than in the raw data will be presented when reporting SD.
- Categorical/discrete variables: the frequency count and the percentage (of available data) for each class of the variable will be presented and will be displayed in the form XX (XX.X%) where the percentage is in the parentheses. All percentages will be presented to 1 decimal place, unless otherwise specified. Percentages equal to 100 will be reported as 100% and percentages will not be presented for zero frequencies. Unless otherwise specified, percentages will be calculated based on the number of patients specified by the appropriate population definition.

- Date variables: formatted as DDMMYY for presentation. Time will be formatted in military time as HH:MM for presentation.

Extra measurements (such as unscheduled or repeat assessments) will not be included in summary tables but will be included in patient listings. They will be used in summary tables which are not ‘time specific’, for example, summaries of maximum post dose values.

All tables, listings, figures will be produced in landscape orientation using Times New Roman 9-point font. Output files will be created in rich text file (RTF) format.

Missing or invalid data will be generally treated as missing, not imputed, unless otherwise stated (see Section 9.5).

The table, figures and listing shells and table of contents as part of this SAP provide the expected layout and titles of the tables, listings and figures. Any changes to format, layout, titles, numbering, or any other minor deviation will not necessitate a revision to the SAP nor will it be considered a deviation from planned analyses. Only true differences in the analysis methods or data handling will necessitate such documentation. The appropriate listings supporting the tables will be included and are not specified in the individual sections throughout the document.

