## **11. EFFICACY ANALYSIS**

The response criteria for this study are from the Revised International Working Group (IWG) Response Criteria (2006). These criteria are described in detail in Appendix F of the protocol.

Response categories include CR: Complete Response, CR marrow: Marrow CR, PR: Partial Remission, Stable Disease, Failure, Relapse after CR or PR, and Not Evaluated / Missing.

The best objective response for each patient will be summarized by number and percentage.

In addition, cytogenetic responses were collected and include: Complete, Partial, Stable Disease, Failure – Death, Failure – Disease Progression, and Response Not Available. The best cytogenetic response for each patient will be summarized by number and percentage.

Hematological Improvement responses were collected and include N/A, Erythroid Response, Platelet Response, Neutrophil Response, Progression or Relapse after HI, and Response Not Available. Because these data were collected as ‘check all that apply’ (instead of select one), hematological improvement data will be presented in patient listings format.

In addition to the summary tables, efficacy data will also be presented in the individual patient listings.

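### SAP 11 reports response in cohorts of 3 or 4 without the exact 95% confidence intervals of protocol 11.9, does not tabulate the composite CRR, and does not record the change in SAP 16

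*SAP*

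**What the plan says.** Protocol 11.9 specifies the response summary: "CRR will be summarized by number and percentage of patients meeting the definition of CRR along with the corresponding exact 95% confidence intervals". It also attaches 95% intervals to hematological improvement (HI) and the rate of transfusion independence, and does not limit any of this to Phase 2. CRR is a Phase 1b secondary objective in protocol 3.1 and SAP 3.2, so the requirement reaches the 20 patients enrolled.

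Protocol 11.1 describes the whole analysis as mainly descriptive: "No formal statistical hypothesis testing is planned". It lets the SAP modify the planned analyses, provided the SAP documents the change clearly.

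SAP 11 says: "The best objective response for each patient will be summarized by number and percentage". Best cytogenetic response is treated the same way, and HI goes to listings only. CI is defined in the SAP's abbreviation list, but no analysis section uses it. The bold note in SAP 1 rules out inferential methods for efficacy because of low enrolment. SAP 15.1 extends this to safety and adds early termination as a reason: "Due to the early termination of this study and low sample size, efficacy and safety endpoints will not be analyzed via inferential statistical methods". SAP 16, the section for changes from the protocol, lists none; it says only that the SAP supersedes the protocol's statistical text.

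Two table rules also matter. Under SAP 8.1, "a row with all zeros will not appear", with an exception only for study-termination tables. Under SAP 8.4, "percentages will not be presented for zero frequencies".

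**The concern.** The reason given does not fit what is lost. The protocol planned no hypothesis tests, so for response a switch to descriptive output takes away only the intervals. An exact binomial interval keeps at least its nominal coverage at any sample size, and a small sample is where a bare percentage misleads most. A reader of the synoptic report would see figures such as 33% or 25% in one cohort column beside 0 in the next, with nothing to show that these are statistically indistinguishable.

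The endpoint itself is missing as well. CRR counts a patient with CR, CRi, marrow CR, PR or HI. SAP 11 has no CRi category and leaves HI in listings, so its tables do not yield the rate named in the objective. A category with no patients in the whole study would also be absent from the summary table, although 0/20 carries information.

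**Working it through.** **The plan's own response calculation.** The only one is the Phase 2 Simon design (stop if 1 or fewer of 15 respond; success if 6 or more of 25). With b the binomial probability,

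P(success | p) = sum over x = 2 to 15 of b(x; 15, p) × P[Bin(10, p) ≥ 6 − x].

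This gives 0.802 at p = 0.30 and 0.033 at p = 0.10, consistent with the stated 80% power and within the 0.05 limit. The design is sound, but no patient entered Phase 2 and the present point does not depend on it.

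**Inputs.** Cohort sizes from SAP 8.1: 3, 3, 3, 4, 3 and 4, total 20. Confidence level from protocol 11.1: two-sided 95%. Interval type from protocol 11.9: exact. The documents give no results, so the response counts below are illustrations.

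**Formula (Clopper-Pearson), x responders of n.**
- Lower limit = 2.5% quantile of Beta(x, n − x + 1); 0 if x = 0.
- Upper limit = 97.5% quantile of Beta(x + 1, n − x); 1 if x = n.
- Closed forms: for x = 0 the upper limit is 1 − 0.025^(1/n); for x = 1 the lower limit is 1 − 0.975^(1/n).

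For example, 0/20 gives 1 − 0.025^(1/20) = 0.168, and the lower limit for 1/3 is 1 − 0.975^(1/3) = 0.008.

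| x/n | Shown by SAP 11 | Exact 95% interval |
|---|---|---|
| 0/3 | 0, no percentage | 0 to 70.8% |
| 1/3 | 33.3% | 0.8 to 90.6% |
| 0/4 | 0, no percentage | 0 to 60.2% |
| 1/4 | 25.0% | 0.6 to 80.6% |
| 0/20 | row omitted | 0 to 16.8% |
| 5/20 | 25.0% | 8.7 to 49.1% |

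The cohort intervals in the table span about 60 to 90 percentage points. The 5/20 interval contains both the 10% null and the 30% alternative of the Phase 2 design; the bare 25% does not show that.

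**Zero rows.** SAP 8.1 removes a row only if it is zero in all six cohorts and the Total. The relevant probability is therefore P(0 of 20) = (1 − p)^20. The true rate p for a category is an assumption:
- p = 5%: 0.95^20 = 0.358
- p = 10%: 0.9^20 = 0.122
- p = 20%: 0.8^20 = 0.012

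**The case against.** The strongest reply is that little hangs on this. The study was closed after a portfolio review, nobody entered Expansion or Phase 2, the output is a synoptic report, and no decision rule uses these percentages. The move to descriptive output is disclosed in SAP 1 and 15.1, and the protocol allows the SAP to change analyses. Anyone can compute an interval from the printed count and N.

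The low stakes stand. The rest stands only in part. The disclosure never mentions intervals or protocol 11.9, and SAP 16 is silent. A reader can rebuild an interval for a single tabulated category, but not for CRR, which would first have to be assembled from the listings.

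A reader might also infer more than the documents support:
- *That null results vanish from the report.* They do not. A zero in one cohort stays as a count if any other cohort has a patient in that category, and full listings are kept.
- *That none observed cannot be told from not assessed.* SAP 8.1 says the tables show the number of patients concerned and separate unknown or not performed from missing. SAP 11 has a category for not evaluated or missing. With one best response per patient and a fixed N, an absent row means 0 of N.
- *That an interval for DLTs, or pooled decitabine and azacitidine columns, was dropped.* Neither document plans either.
- *That the SAP expressly deletes the intervals because of sample size alone.* They lapse by omission under a general sentence, and SAP 15.1 names early termination first.

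**Conclusion.** The concern holds in a limited form. Protocol 11.9's exact 95% intervals for response are absent from the SAP, the composite CRR is not tabulated, and SAP 16 records neither change although protocol 11.1 requires documentation. Low sample size does not justify the omission, because the intervals were part of a plan without tests and are valid at any n. In size, cohort percentages would stand without intervals that are about 60 to 90 points wide, and a Total of 5/20 without one of 8.7 to 49.1%.

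The zero-row effect is secondary: it affects only a category empty across all 20 patients, about a 12% chance at a true rate of 10% (36% at 5%, 1% at 20%).

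The calculations assume that all 20 enrolled patients are in the Safety population, that the column N is the denominator and, for the zero-row figure, that patients are independent with a common rate. No study decision changes; the reporting of the one planned efficacy summary does.

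**What to change.** - **SAP 11:** derive CRR per patient. HI was collected as check-all-that-apply, so define a patient as having HI if any of the erythroid, platelet or neutrophil responses is recorded. State how CRi is handled, since neither SAP 11 nor protocol Appendix F has a CRi category. Keep the protocol 11.9 rule that patients without marrow for assessment count as non-responders. Report CRR and CR as number, percentage and exact (Clopper-Pearson) 95% interval for the Total and for each displayed cohort column.
- **SAP 8.1 and 8.4:** extend the zero-row exception to every response category named in SAP 11, and print the percentage for a zero count in those rows.
- **SAP 15.1 and the matching note in SAP 1:** reword to say that there are no hypothesis tests and that response estimates are given with exact 95% intervals.
- **SAP 16:** record any departure from protocol 11.9 that remains, including the intervals for hematological improvement and transfusion independence if they are not produced.

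The cost is one derived variable, a small amount of table programming and a few sentences of SAP text, with no new data. SAP 1 says the plan is finalized before database lock, so that is the point to make the change. The drawback is that wide intervals make the reported rates look less favourable.
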